8.3 Subgroup Analyses

Subgroup analyses will be performed by the following items for the percent change in LDL-C from baseline to Week 12, the primary endpoint. Using the same analysis of covariance as for the primary analysis, the least squares mean for each treatment group and the differences in the mean of the least squares between each ETC-1002 group and the placebo group, together with the two-sided 95% confidence intervals, will be calculated for each subgroup. In the analysis for the statin response subgroup, the randomization stratification factor (statin response) will not be included in the model.

- Statin response (statin tolerance, statin intolerance)
- Sex (male, female)

- Familial hypercholesterolemia (yes, no)
- Diabetes mellitus (yes, no)
- Age (<65 years, \geq 65 years)
- Statin use (yes, no)

9 Safety Analyses

Tabulation by treatment group (by dose and overall for ETC-1002) will be performed in the safety analysis set. Baseline is defined as the last data before the start of IMP administration in the treatment period. The same tabulation will be performed by the randomization stratification factor (statin response). In addition to analysis for the specified visit, an additional analysis will be conducted at Week 12 with missing data being imputed based on the LOCF principle (Week 12 [LOCF]). The procedure for imputation will be the same as that for efficacy endpoints.

9.1 Extent of Exposure

Descriptive statistics will be calculated for the duration of IMP treatment in the treatment period (Date of final IMP administration in the treatment period – Date of initial IMP administration in the treatment period + 1) and for the total number of days of IMP administration in the treatment period (The total number of days of taking 3 tablets of the IMP in the treatment period).

9.2 Adverse Events

All AEs will be coded by system organ class (SOC) and preferred term (PT) using Medical Dictionary for Regulatory Activities (MedDRA) version 24.1. The incidence of the following events will be calculated by SOC, by PT, and overall. If a subject experiences the same event more than once, the more severe event will be used.

- Treatment-emergent AEs
- TEAEs by severity
- TEAEs with an outcome of death
- Serious TEAEs
- TEAEs leading to discontinuation of the IMP

TEAEs potentially causally related to the IMP will be summarized in the same manner. Summary tables only for events occurring in 2 or more subjects in any group will be prepared for TEAEs and for TEAEs potentially causally related to the IMP.

9.2.1 AEs of special interest

The incidence of AEs of special interest will be calculated by SOC and by PT. AEs of special interest potentially causally related to the IMP will be summarized in the same manner. The classification of AEs of special interest is shown in [REDACTED].

9.3 Clinical Laboratory Data

Among parameters of the urinalysis in the laboratory tests, the qualitative urinalysis includes parameters other than pH and specific gravity.

For parameters other than qualitative urinalysis, descriptive statistics of the actual value and change from baseline will be calculated at each visit. For qualitative urinalysis parameters, shift tables at each visit from baseline will be prepared. For parameters other than qualitative urinalysis, measured values will be categorized using the reference range to “below the lower limit of reference range”, “within the reference range” and “above the upper limit of reference range”, and shift tables at each visit from baseline will be prepared.

The number and percentage of subjects meeting the criteria for identifying laboratory values of potential clinical relevance ([Appendix 2: Criteria for Identifying Laboratory Values of Potential Clinical Relevance](#)) will be calculated.

9.4 Vital Sign Data

For vital signs (blood pressure, pulse rate, and body temperature), descriptive statistics of the actual value and change from baseline will be calculated at each visit.

The number and percentage of subjects meeting the criteria for identifying vital signs of potential clinical relevance ([Appendix 1: Criteria for Identifying Vital Signs and Weight of Potential Clinical Relevance](#)) will be calculated.

9.5 Physical Examination Data

Physical findings recorded in the CRF will be presented in a listing of subjects.

9.6 Electrocardiogram Data

For ECG parameters (heart rate, PR interval, RR interval, QRS interval, QT interval, and QTcF), descriptive statistics of the actual value and change from baseline will be calculated at each visit.

The number and percentage of subjects with a QTcF of >450 msec, >480 msec, or >500 msec at any postdose visit will be calculated. In addition, the number and percentage of subjects who have a change in QTcF from baseline of >30 msec or

>60 msec at any postdose visit will be calculated. The number and percentage of subjects meeting these criteria at each postdose visit will also be calculated.

For assessment of normality/abnormality, shift tables at each visit from baseline will be prepared.

The number and percentage of subjects meeting the criteria for identifying ECG measurements of potential clinical relevance ([Appendix 3: Criteria for Identifying ECG Measurements of Potential Clinical Relevance](#)) will be calculated.

9.7 Other Safety Data

9.7.1 Body weight

Descriptive statistics of the actual value and change from baseline will be calculated at each visit.

The number and percentage of subjects meeting the criteria for identifying body weight of potential clinical relevance ([Appendix 1: Criteria for Identifying Vital Signs and Weight of Potential Clinical Relevance](#)) will be calculated.

10 Pharmacokinetic Analyses

For the PK analysis set, descriptive statistics (number of subjects, number of subjects actually analyzed, mean, standard deviation, coefficient of variation, minimum, median, and maximum) will be calculated for the plasma concentrations of ETC-1002 and its active metabolite ESP15228 at each dose, visit, and postdose time point (before or at 2 to 4 hours after administration at each visit). In the calculation of descriptive statistics, plasma drug concentrations below the lower limit of quantitation will be regarded as “0” (zero).

Timecourse plots of the plasma drug concentrations of ETC-1002 and its active metabolite ESP15228 before administration at each visit will be prepared (horizontal axis: visit, longitudinal axis: plasma drug concentration). The mean \pm standard deviation of plasma drug concentrations before administration at each visit calculated by dose and by visit will be plotted. Similarly, the individual timecourses for all subjects will be plotted by dose.

11 Pharmacodynamic Analyses

No pharmacodynamic analysis is planned.

12 Pharmacogenomic Analyses

No pharmacogenomic analysis is planned.

13 Interim Analysis

No interim analysis is planned.

14 Changes in the Planned Analyses

Regarding the definition of the pharmacokinetic analysis set in [Section 5.3](#), since measurement results of plasma drug concentration will not be available at the time of unblinding, an equivalent analysis set is defined based on available records on the time of blood sampling.

Regarding the following calculations for QTcF in ECG in [Section 9.6](#), calculations at baseline that were planned in the protocol will not be performed.

- The number and percentage of subjects with a QTcF of >450 msec, >480 msec, or >500 msec at any postdose time point will be calculated.
- The number and percentage of subjects who have a change in QTcF from baseline of >30 msec or >60 msec at any postdose time point will be calculated.

15 References

Not applicable.

Appendix 1 Criteria for Identifying Vital Signs and Weight of Potential Clinical Relevance

Variable	Criterion Value ^a	Change Relative to Baseline ^a
Pulse Rate	>120 bpm <50 bpm	≥15 bpm increase ≥15 bpm decrease
Systolic Blood Pressure	>160 mmHg <90 mmHg	≥20 mmHg increase ≥20 mmHg decrease
Diastolic Blood Pressure	>100 mmHg <50 mmHg	≥15 mmHg increase ≥15 mmHg decrease
Weight	N/A	≥7% increase ≥7% decrease

^aIn order to be identified as potentially clinically relevant, an on-treatment value must meet the “Criterion Value” and also represent a change from the subject’s baseline value of at least the magnitude shown in the “Change Relative to Baseline” column.

Appendix 2 **Criteria for Identifying Laboratory Values of Potential Clinical Relevance**

Laboratory Tests	Criteria
Chemistry	
AST	$\geq 3 \times$ upper limit of normal (ULN)
ALT	$\geq 3 \times$ ULN
Bilirubin, Total	$\geq 2 \times$ ULN
ALP	$\geq 3 \times$ ULN
Urea Nitrogen	≥ 30 mg/dL
Creatinine	≥ 2.0 mg/dL
Creatine Kinase (CK)	$\geq 4 \times$ ULN
Uric Acid	≥ 9 mg/dL
Hematology	
Hematocrit	
Males	$\leq 37\%$ and ≥ 3 percentage points decrease from baseline
Females	$\leq 32\%$ and ≥ 3 percentage points decrease from baseline
Hemoglobin	
Males	≤ 11.5 g/dL
Females	≤ 9.5 g/dL
Leukocyte Count	$\leq 2,800/\text{mm}^3$ or $\geq 16,000/\text{mm}^3$
Platelet Count	$\leq 75,000/\text{mm}^3$ or $\geq 700,000/\text{mm}^3$
Urinalysis	
Protein	Increase of ≥ 2 units
Glucose	Increase of ≥ 2 units
Additional Criteria	
Chloride	≤ 90 mEq/L or ≥ 118 mEq/L
Potassium	≤ 2.5 mEq/L or ≥ 6.5 mEq/L
Sodium	≤ 126 mEq/L or ≥ 156 mEq/L
Calcium	≤ 8.2 mg/dL or ≥ 12 mg/dL
Glucose	
Fasting	≥ 126 mg/dL
Non-fasting	≥ 200 mg/dL
Total Cholesterol, Fasting	≥ 240 mg/dL
LDL Cholesterol, Fasting	≥ 160 mg/dL
HDL Cholesterol, Fasting	< 40 mg/dL
Triglycerides, Fasting	≥ 150 mg/dL

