5.2.1 Inclusion Criteria

Subjects are required to meet the following inclusion criteria when assessed:

- 1) Patients from whom written informed consent is obtained prior to start of the trial
- 2) Patients, either male or female, age 20 years or older and younger than 75 years at the time of informed consent
- 3) Patients who meet the following criteria for statin tolerance or statin intolerance
 - Statin tolerance
Patients with hypercholesterolemia who have been taking statins (atorvastatin, pitavastatin, rosuvastatin, pravastatin, simvastatin, or fluvastatin) and hypercholesterolemia drugs other than statins if necessary, at the same dose and regimen from at least 4 weeks prior to Week -5 (Visit S1) (at least 6 weeks, for fibrates and selective PPAR α modulators) to Week -5 (Visit S1) according to the approved regimen, but fail to achieve the lipid management goals of LDL-C based on risk assessment shown in the inclusion criteria 4) at both Week -5 (Visit S1) and Week -1 (Visit S3)
 - Statin intolerance
Patients with hypercholesterolemia in whom safety problems occurred when administration of statins was started or increased in dose and were resolved after discontinuation or dose reduction of statin administration, and who have been taking statins at (or below) the lowest approved daily dose and/or who have been taking at least one hypercholesterolemia drug other than statins at the same dose and regimen from at least 4 weeks prior to Week -5 (Visit S1) (at least 6 weeks, for fibrates and selective PPAR α modulators) to Week -5 (Visit S1) according to the approved dosage regimen, but fail to achieve the lipid management goals of LDL-C based on risk assessment shown in the inclusion criteria 4) at both Week -5 (Visit S1) and Week -1 (Visit S3)
- 4) Patients considered to be at risk of developing cardiovascular events who meet any of the following conditions a), b), or c)
 - a) Patients with either of the following medical histories or complications and in whom LDL-C at Week -5 (Visit S1) and Week-1 (Visit S3) is ≥ 100 mg/dL
 - History of coronary artery disease
 - Diagnosed with heterozygous familial hypercholesterolemia (HeFH)

- b) Patients with any of the following medical histories or complications and in whom LDL-C at Week -5 (Visit S1) and Week-1 (Visit S3) is ≥ 120 mg/dL
 - Diagnosed with peripheral arterial disease
 - History of non-cardiogenic cerebral infarction

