 - Diagnosed with chronic kidney disease and does not fall under the exclusion criteria 12)
 - Diagnosed with type 2 diabetes mellitus more than 3 months prior to Week -5 (Visit S1) and does not fall under the exclusion criteria 7)
- c) Patients who do not meet inclusion criteria a) or b), but whose total score in the coronary artery disease risk prediction model using the Saita score specified by the Japan Atherosclerosis Society is ≥ 41 and ≤ 55 points (intermediate risk) and in whom each LDL-C level at Week -5 (Visit S1) and Week -1 (Visit S3) is ≥ 140 mg/dL, or whose total score is ≥ 56 (high risk) and in whom each LDL-C level at Week -5 (Visit S1) and Week -1 (Visit S3) is ≥ 120 mg/dL

- 5) Patients with fasting TG level of <400 mg/dL at Week -5 (Visit S1)
- 6) Patients with body mass index (BMI) of ≥ 18 kg/m² and <35 kg/m² at Week -5 (Visit S1)

[Rationale for inclusion criteria]

- 1) This criterion is set from ethical considerations.
- 2) Since elderly patients generally have reduced physiological function and ETC-1002 is administered to Japanese patients with hypercholesterolemia for the first time, the trial is to be conducted in patients aged <75 years in consideration of safety. The lower limit of age is set at 20 years from ethical considerations.
- 3) to 4) These criteria are set to appropriately evaluate the efficacy.
- 5) This criterion is set in consideration of the difficulty in accurate calculation of LDL-C using the Friedewald formula and subject safety.
- 6) This is set to minimize the inter-individual variation in pharmacokinetics due to body size.

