5.2.2 Exclusion Criteria

Subjects will be excluded if they meet any of the following exclusion criteria when assessed:

- 1) Women who are pregnant or breastfeeding or who have a positive pregnancy test (urine) result at Week -5 (Visit S1) or Day 1 (Visit T1)
- 2) Sexually active male subjects or sexually active female subjects of childbearing potential who do not agree to practice 2 different approved methods of birth

control or to maintain complete abstinence (the methods of periodic abstinence and withdrawal are not appropriate for contraception) during the trial and for 30 days after final IMP administration. If employing birth control, 2 of the following methods must be used: vasectomy, tubal ligation, intrauterine device, birth control pill, and condoms (all methods are approved or certified in Japan). A definition of childbearing potential can be found in [Section 10.3](#).

- 3) Patients with homozygous familial hypercholesterolemia (HoFH)
- 4) Patients with a history or current symptoms of any of the following cardiovascular diseases within 3 months prior to Week -5 (Visit S1), or with any of the following AEs during the screening [REDACTED] period
 - Myocardial infarction, severe or unstable angina pectoris, coronary angioplasty, coronary artery bypass graft, stroke, transient ischemic attack, symptomatic carotid artery stenosis, symptomatic peripheral arterial disease, or decompensated heart failure
 - Abdominal aortic aneurysm
 - Unexplained syncope or long-QT syndrome, family history of long-QT syndrome, or risk factors for Torsade de Pointes, such as persistent hypokalemia or second- or third-degree atrioventricular block (except when controlled by medication, etc)
- 5) Patients with uncontrolled hypertension, defined as follows: sitting systolic blood pressure of ≥ 160 mmHg or diastolic blood pressure of ≥ 100 mmHg after resting 5 minutes at Week -5 (Visit S1)
- 6) Patients with uncontrolled and serious hematologic or coagulation disorders or with Hgb of < 10.0 g/dL at Week -5 (Visit S1)
- 7) Patients with type 1 diabetes or uncontrolled type 2 diabetes with HbA1c of $\geq 9\%$ at Week -5 (Visit S1)
- 8) Patients with uncontrolled hypothyroidism with thyroid-stimulating hormone (TSH) of $> 1.5 \times$ the upper limit of normal (ULN) at Week -5 (Visit S1)
- 9) Patients with liver disease or dysfunction, including:
 - Positive serology for hepatitis B surface antigen (HBsAg) or hepatitis C (HCV) antibodies at Week -5 (Visit S1)

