- CT-10.2.1-2 Shift Tables of Clinical Laboratory Test Results by Statin Response - Serum Chemistry (Safety Analysis Set)
- CT-10.2.2-1 Shift Tables of Clinical Laboratory Test Results - Hematology (Safety Analysis Set)
- CT-10.2.2-2 Shift Tables of Clinical Laboratory Test Results by Statin Response - Hematology (Safety Analysis Set)
- CT-10.2.3-1 Shift Tables of Clinical Laboratory Test Results - Urinalysis (Safety Analysis Set)
- CT-10.2.3-2 Shift Tables of Clinical Laboratory Test Results by Statin Response - Urinalysis (Safety Analysis Set)
- CT-10.2.4-1 Shift Tables of Clinical Laboratory Test Results - Qualitative Urinalysis (Safety Analysis Set)
- CT-10.2.4-2 Shift Tables of Clinical Laboratory Test Results by Statin Response - Qualitative Urinalysis (Safety Analysis Set)

- CT-10.3-1 Incidences of Potentially Clinically Significant Abnormalities in Laboratory Tests (Safety Analysis Set)
- CT-10.3-2 Incidences of Potentially Clinically Significant Abnormalities in Laboratory Tests by Statin Response (Safety Analysis Set)
- CT-10.4 Listing of Abnormal Laboratory Findings (Safety Analysis Set)
- CT-11.1-1 Descriptive Statistics for Vital Signs (Safety Analysis Set)
- CT-11.1-2 Descriptive Statistics for Vital Signs by Statin Response (Safety Analysis Set)
- CT-11.2-1 Incidences of Potentially Clinically Significant Abnormalities in Vital Signs (Safety Analysis Set)
- CT-11.2-2 Incidences of Potentially Clinically Significant Abnormalities in Vital Signs by Statin Response (Safety Analysis Set)
- CT-11.3-1 Descriptive Statistics for Body Weight (Safety Analysis Set)
- CT-11.3-2 Descriptive Statistics for Body Weight by Statin Response (Safety Analysis Set)
- CT-11.4-1 Incidences of Potentially Clinically Significant Abnormalities in Body Weight (Safety Analysis Set)
- CT-11.4-2 Incidences of Potentially Clinically Significant Abnormalities in Body Weight by Statin Response (Safety Analysis Set)
- CT-12.1-1 Descriptive Statistics for ECG Parameters (Safety Analysis Set)
- CT-12.1-2 Descriptive Statistics for ECG Parameters by Statin Response (Safety Analysis Set)
- CT-12.2-1 Categorical Analysis of ECG - QTcF (Safety Analysis Set)
- CT-12.2-2 Categorical Analysis of ECG - QTcF by Statin Response (Safety Analysis Set)
- CT-12.3-1 Shift Table of ECG Findings (Normal/Abnormal Assessments) (Safety Analysis Set)
- CT-12.3-2 Shift Table of ECG Findings (Normal/Abnormal Assessments) by Statin Response (Safety Analysis Set)

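### The table of potentially clinically relevant laboratory values (SAP 9.3, Appendix 2) will mix abnormalities present at entry with new ones in the lipid, glucose and male haemoglobin rows

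*SAP*

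**What the plan says.** SAP 9.3 will report "The number and percentage of subjects meeting the criteria for identifying laboratory values of potential clinical relevance", pointing to Appendix 2. It does not say that the value must be post-dose, that the baseline must have been on the other side of the cut-off, or that the value must have worsened. The output is CT-10.3-1, titled "Incidences of Potentially Clinically Significant Abnormalities in Laboratory Tests (Safety Analysis Set"), with a version by statin response (CT-10.3-2).

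Within Appendix 2, only haematocrit (which needs a "3 percentage points decrease from baseline") and urine protein and urine glucose (each an increase of at least 2 units) depend on baseline. Every other row is a bare threshold, including "LDL Cholesterol, Fasting".

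The two neighbouring appendices work differently. For vital signs (Appendix 1), an on-treatment value must pass the criterion and must also differ from the "baseline value of at least the magnitude shown in the" change column. Appendix 3 (ECG) carries the same footnote; Appendix 2 has none.

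Protocol 5.2.1 enrols subjects who "fail to achieve the lipid management goals of LDL-C based on risk assessment" and "Patients with fasting TG level of <400 mg/dL". Protocol 5.2.2 excludes "uncontrolled and serious hematologic or coagulation disorders or with Hgb of" less than 10.0 g/dL.

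**The concern.** A subject who enters past a cut-off and does not change can be counted as an abnormality in a table labelled as incidence. The reader of the study report wants to know how many subjects developed an abnormality on each dose. If a large share of the count was there before the first dose, the table answers another question, and in groups of about 44 a genuine difference in new abnormalities is easier to miss. The entry criteria make this likely for some rows, since the trial selects for high LDL-C and accepts raised triglycerides and type 2 diabetes.

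**Working it through.** The plan states no figure for this table, so there is none to reproduce.

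**Step 1: count the rows.** Appendix 2 has 26 criterion rows covering 23 tests. Tied to baseline: haematocrit (men, women), urine protein and urine glucose, which is 4 rows or 3 tests. Absolute: 26 − 4 = 22 rows (85%), or 23 − 3 = 20 tests (87%).

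**Step 2: compare the cut-offs with the entry limits (Protocol 5.2.1, 5.2.2).**

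| Row | Appendix 2 cut-off | Entry limit | Can be met at entry? |
|---|---|---|---|
| LDL-C | ≥160 mg/dL | floor of 100, 120 or 140 by risk; no ceiling | yes |
| Total cholesterol | ≥240 mg/dL | none | yes |
| HDL-C | <40 mg/dL | none | yes |
| Triglycerides | ≥150 mg/dL | <400 mg/dL | yes, from 150 up to 400 |
| Glucose | ≥126 fasting, ≥200 non-fasting | type 2 diabetes qualifies; HbA1c ≥9% excluded; no glucose limit | yes |
| Haemoglobin, men | ≤11.5 g/dL | <10.0 excluded | yes, 10.0 to 11.5 |
| Haemoglobin, women | ≤9.5 g/dL | <10.0 excluded | no |
| Urea nitrogen, uric acid | ≥30 mg/dL, ≥9 mg/dL | none; chronic kidney disease qualifies | possibly |
| AST, ALT | ≥3 × ULN | ≥3 × ULN excluded | no |
| Bilirubin | ≥2 × ULN | ≥2 × ULN excluded | no |
| CK | ≥4 × ULN | >3 × ULN excluded | no |

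These laboratory exclusions apply at Week −5, so a few subjects could still drift past a cut-off before Day 1.

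**Step 3: what pre-existing cases do to a contrast.** Let p be the share that meets a criterion at baseline and stays flagged, and r the new-onset rate among the rest. The count as written is p + (1 − p)r. Assume p = 30%, r = 5% on placebo and 20% on active:

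- placebo: 30 + 0.7 × 5 = 33.5%
- active: 30 + 0.7 × 20 = 44%

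The ratio shown is 44/33.5 = 1.3. Among subjects at risk it is 20/5 = 4. The difference falls from 15 to 0.7 × 15 = 10.5 percentage points. These rates are invented to show the mechanism.

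**Step 4: LDL-C row, illustration only.** The documents give no baseline distribution. For a normal baseline truncated at a floor of 100, the share at or above 160 is [1 − Φ((160 − μ)/σ)] / [1 − Φ((100 − μ)/σ)]:

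- mean 130, SD 20: 0.0668/0.9332 = 7.2%
- mean 140, SD 25: 0.2119/0.9452 = 22.4%
- mean 150, SD 30: 0.3694/0.9522 = 38.8%

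A simulation then followed subjects through the five post-baseline visits (Weeks 2, 4, 6, 8 and 12). Assumptions: underlying LDL-C before selection normal with mean 110 to 150 and SD 30; within-subject CV 8%; the entry floor met at two screening visits; individual percent response with SD 15 around a mean of 0 (placebo) or −19 (the plan's assumed effect). A subject is flagged if any post-dose value is at least 160. Counts are per 44 subjects; shares come from unrounded counts.

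| Floor / mean | ≥160 at baseline | Placebo: flagged, of which new | Already met | Active: flagged, of which new | Already met |
|---|---|---|---|---|---|
| 100 / 110 | 4.6 | 11.5, 8.2 | 29% | 3.1, 1.6 | 48% |
| 120 / 130 | 13.7 | 22.9, 12.2 | 47% | 8.3, 3.0 | 63% |
| 140 / 150 | 28.5 | 33.6, 9.5 | 72% | 16.5, 3.1 | 81% |

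Across all nine combinations of floor and mean, the already-met share runs from 29% to 72% on placebo and from 48% to 81% on active. Nothing comparable was computed for triglycerides, glucose or haemoglobin.

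**The case against.** The other side has several sound points.

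- **Other outputs use baseline.** LDL-C and the other lipids get baseline-adjusted analyses of percent change and descriptive change by visit (SAP 8.1.1, 8.2). Glucose and haemoglobin get change from baseline and shift tables (SAP 9.3), and CT-10.4 lists abnormal findings. This stands as mitigation. It is not a full answer: the shift tables use the reference range, not the Appendix 2 cut-offs, so a subject above the upper glucose limit at baseline stays in the same category after any further rise.
- **Absolute thresholds appear elsewhere.** SAP 9.6 counts QTcF above 450, 480 and 500 msec without a baseline condition. True, but it specifies post-dose visits and tabulates change from baseline alongside.
- **Randomization balances the background in expectation.** Agreed. The harm is dilution and a misleading label, not systematic bias between arms.
- **Excluding subjects abnormal at baseline would lose information.** A man falling from 11.4 to 8.5 g/dL, or a subject rising from glucose 130 to 300 mg/dL, could then never be counted. This stands, and it decides the form of the fix.

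A reader might also infer that a subject past a cut-off at entry is flagged at every visit, and equally in every arm. The documents do not support that for LDL-C: at the plan's assumed effect, 165 mg/dL becomes 165 × 0.81 = 134, below the cut-off. For LDL-C and total cholesterol, effective treatment lowers the count, so those rows partly repeat the efficacy result.

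**Conclusion.** The point holds for a defined set of rows: LDL-C, total cholesterol, HDL-C, triglycerides, glucose, haemoglobin in men between 10.0 and 11.5 g/dL, and possibly urea nitrogen and uric acid. There CT-10.3 will not separate new abnormalities from those present before dosing. That the rows can overlap with eligibility follows from the documents alone. How many subjects are involved does not, because no baseline distribution is given; the LDL-C percentages rest wholly on the stated assumptions.

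A stronger reading would be that the whole laboratory safety evaluation is compromised, including the liver and muscle signals. The documents do not support it: AST, ALT, bilirubin and CK are screened at or below their Appendix 2 cut-offs. This is a descriptive table; the primary analysis, its error control and the sample size are untouched. It is a worthwhile, inexpensive improvement to make before unblinding.

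**What to change.** In SAP 9.3, state that only post-dose values count, and present each Appendix 2 criterion by baseline status: met or not met at the safety baseline, which SAP 3.4 already defines as the last value before the first dose of the treatment period. Use the number of subjects at risk in each stratum as denominator. Report the not-met stratum as the new-onset incidence. Keep the all-subject count and the met-at-baseline stratum in the table, so that subjects already abnormal remain visible and their worsening can be followed up. The rows already tied to a change can stay as they are defined.

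No new data are needed. The cost is a small programming change and a longer table. New-onset denominators may be materially smaller in the lipid rows: in the illustration above, 44 − 4.6 = 39.4 down to 44 − 28.5 = 15.5 subjects per group for LDL-C.
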